8.6.4 Pregnancy

Since TIN816 has not been tested in reproductive toxicity studies to date, the teratogenicity potential of TIN816 is not known. Therefore, if a female study participant becomes pregnant, the pregnancy consent form should be presented to the study participant. The participant must be given adequate time to read, review and sign the pregnancy consent form. This consent form is necessary to allow the investigator to collect and report information regarding the pregnancy. To ensure participant safety, each pregnancy occurring after signing the informed consent must be reported to Novartis within 24 hours of learning of its occurrence.

Details of all pregnancies in female participants will be collected after the start of study treatment and until the 90 day visit.

While pregnancy itself is not considered to be an AE or SAE, any pregnancy complication or elective termination of a pregnancy for medical reasons will be reported as an AE or SAE.

Abnormal pregnancy outcomes (e.g. spontaneous abortion, fetal death, stillbirth, congenital anomalies, ectopic pregnancy) are considered SAEs and will be reported as such.

Any post study pregnancy-related SAE considered reasonably related to the study treatment by the investigator will be reported to Novartis as described in [Section 8.6.3](#). While the investigator is not obligated to actively seek this information in former study participants, he or she may learn of an SAE through spontaneous reporting.

The pregnancy should be followed-up to determine outcome, including spontaneous or voluntary termination, details of the birth, and the presence or absence of any birth defects, congenital abnormalities, or maternal and/or newborn complications.

Pregnancy should be recorded and reported by the investigator to the Novartis chief medical office and patient safety (CMO&PS). Pregnancy follow-up should be recorded on the same form and should include an assessment of the possible relationship to the study treatment and any pregnancy outcome. Any SAE experienced during pregnancy must be reported.

After consent is provided, the pregnancy reporting will occur up to one year after the estimated date of delivery.

8.6.5 Disease-related events and/or disease-related outcomes not qualifying as AEs or SAEs

Not Applicable

8.6.6 Adverse events of special interest

The following are adverse events of special interest:

Bleeding

TIN816 ability to decrease ADP levels can reduce ADP and thrombin-induced platelet aggregation and is linked to a potential risk of increased bleeding. In the FIH study cohorts 1-

4, inhibition of ADP-induced platelet aggregation was seen in ex vivo whole blood aggregometry assay and was not associated with bleeding AE. In one participant in cohort 3 at 1.0 mg/kg that suffered from trauma and had subsequent surgeries, no abnormal bleeding nor hemorrhage were seen during and after surgical interventions despite inhibition of ex vivo ADP-induced platelet aggregation. In cohort 4 at 2.0 mg/kg, compared to placebo and baseline, no increase in bleeding/clotting time was noted in 5 out of 6 participants receiving TIN816, although a slight increase in closure time was noted up to 2 weeks after TIN816 administration in the ex vivo platelet function assay using a P2Y cartridge. One participant had a slight increase in bleeding/clotting time from baseline to Day 8 (within normal range) and returned to normal values by Day 15.

Standard coagulation tests (including PT, PTT and INR) should be monitored. In the CTIN816B12201 study, TIN816 will not be used in participants who are receiving dual antiplatelet agents; therefore, these participants will be excluded from study participation. In addition, adequate monitoring of respective coagulation parameters will be done in study participants.

Perivascular/vascular mineralization

Perivascular/vascular mineralization of minimal to mild severity was observed in minipig. In the FIH study cohorts 1-4, there was no change in serum calcium nor serum phosphorus noted. No changes were observed in kidney function markers (e.g., eGFR) and no abnormalities were seen in urine dipstick parameters (protein, blood glucose, ketones, bilirubin, urobilinogen, pH, leukocyte esterase, specific gravity). There was no change in cardiovascular parameters (blood pressure, ECG) or joint AE pointing to mineralization.

In the CTIN816B12201 study, the risk is minimized by administration of single dose only and ensuring an appropriate safety margin and dose which was tested in healthy volunteers. In addition, serum calcium, phosphorus and free pyrophosphate levels should be monitored in study participants.

Infusion reactions and hypersensitivity

Injection of a foreign protein into humans may trigger immune response with or without inflammatory signs and symptoms. Such reactions, if they occur, may be immediate or delayed up to several weeks. Since TIN816 is a modified version of a naturally occurring human protein, immunogenicity may occur.

The CTIN816B12201 study will apply single dosing. A prolonged IV infusion time of 2 hours will reduce C_{max} exposure, and a single dose administration of TIN816 will further reduce the exposure duration. Despite the very low risk of a theoretical infusion reaction due to Monocyte chemoattractant protein-1 (MCP-1) related histamine release, signs and symptoms of any allergic reaction should be closely monitored, and IV infusion could be stopped at any time.

Anti-drug antibody mediated reactions (immunogenicity)

As with other therapeutic recombinant proteins, there is a possibility of TIN inducing an immune response in human participants. Presence of host cell proteins in preclinical and clinical TIN816 batches, is also known to enhance the risk of immunogenicity ([Vanderlaan et al., 2018](#)). The primary consequence of immunogenicity may be altered PK and

PD properties of the drug, leading to a potential loss in efficacy. There is also a theoretical possibility of immune-mediated reactions.

Development of anti-TIN816 antibodies and their neutralization potential of TIN816 and/or endogenous CD39 will be assessed in dedicated plate and cell-based in-vitro assays and are interpreted in the context of PK, PD and safety. Potential reactions related to such antibodies, such as antibody-mediated arthropathy, should be monitored closely.

8.7 Pharmacokinetics

PK serum samples will be collected at the time points defined in the Assessment Schedule ([Table 1-2](#)). Two samples will be collected on Day 1: one sample pre-dose and one sample post-dose within 15 minutes at the end of the two hour study drug infusion. In addition, PK samples should be collected at additional days as indicated in [Table 1-2](#), optimally always at that time point of the day when study drug administration started on Day 1 (e.g. Day 2 sample should be taken 24 h after starting TIN816/placebo infusion).

Instructions regarding sample collection, numbering, processing and shipment are outlined in the Laboratory Manual. The exact time of treatment administration, sample number and time of sample collection are recorded for each sample collected in the eCRF. Sampling problems are to be documented in the eCRF and may include but are not limited to hemolyzed or lipemic samples, insufficient sample volumes, and/or a lack of sample collections.

Pharmacokinetic (PK) samples will be evaluated in all participants treated with TIN816.

TIN816 concentrations will be determined in serum by a validated ligand binding assay with a lower limit of quantification (LLOQ) of approximately 10 ng/mL. The detailed method description of analysis will be given in the method validation report. Concentrations below the LLOQ will be reported as “zero” and missing data will be labeled as such in the Bioanalytical Data Report. Values below the LLOQ will be treated as zero for calculation of PK parameters as well as for summary statistics.

For standard pharmacokinetic abbreviations and definitions refer to Appendix 2 ([Section 10.2](#)) of this protocol. The following pharmacokinetic parameters will be determined from the serum concentration time data using the actual recorded sampling times and non-compartmental method(s) with Phoenix WinNonlin (Version 6.4 or higher): C_{max} , T_{max} , AUC_{last} , AUC_{inf} , $T_{1/2}$, V_z , Cl , and other relevant PK parameters (data permitting).

[figure not shown]
The linear trapezoidal rule will be used for AUC calculation, starting with the initiation of IV infusion. Regression analysis of the terminal elimination phase for the determination of the $T_{1/2}$ will include at least 3 data points after C_{max} . If the adjusted R^2 value of the regression analysis of the terminal phase is less than 0.75, no values will be reported for the corresponding $T_{1/2}$. If the $T_{1/2}$ is not calculable, AUC_{inf} , V_z and CL will not be reported and AUC_{last} will be used.

Urine collected for creatinine clearance as defined in the Assessment Schedule ([Table 1-2](#)) will also be saved for potential urine PK analysis (refer to Creatinine Clearance [Section 8.3.1](#) for additional sample collection details).

TIN816 urine concentrations will be determined by a qualified ligand binding assay. Concentrations below the LLOQ will be reported as “zero” and missing data will be labeled as

such in the Bioanalytical Data Report. Values below the LLOQ will be treated as zero for calculation of PK parameters as well as for summary statistics.

If data permit, renal clearance (CL_r) will be determined using blood and urine TIN816 concentrations, the actual recorded sampling times and non-compartmental method(s) with Phoenix WinNonlin (Version 6.4 or higher).

Sample(s) will be collected at the time point(s) defined in the Assessment Schedule ([Table 1-2](#)).

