This study is designed to assess the PK/PD profile of TIN816 in the participants with SA-AKI. In addition, this study will evaluate safety, tolerability and efficacy of TIN816. Screening will take place during hospitalization in intensive care unit (ICU) or intermediate/high dependency unit (HDU) where potential participants will undergo screening to assess the presence of sepsis and AKI based on sequential organ failure assessment (SOFA) and kidney disease improving global outcomes (KDIGO) scores. A total of approximately 20 participants will be randomized

in the study. Participants will be randomly assigned to receive either TIN816 at 2 milligram (mg)/kg or placebo using a 3:1 allocation ratio (TIN816:placebo). A single dose of the study treatment will be administered via 2-hour intravenous infusion (IV) at the randomization visit in a participant and investigator-blinded fashion. The study treatment must be administered within 48 hours after SA-AKI is first diagnosed, but ideally as soon as possible. PK sample will be taken prior to the study treatment, immediately after the completion of IV infusion at Day 1 and also at Day 2, 3, 5, 8, 14, 30, 60 and 90. All participants will be followed-up for a total duration of 90 days. Safety will be monitored during the entire course of the study; all adverse event (AE) and serious adverse event (SAE) will be collected and reported following standard process and local regulations.

The data generated from this study will be used to support further development of TIN816 for the indication of SA-AKI.

Treatment of interest

TIN816 (human recombinant CD39 enzyme)

Number of Participants:

Approximately 20 participants will be recruited in the study.

Key Inclusion criteria

- ≥ 18 and ≤ 85 years of age.
- Admitted to ICU or intermediate/HDU.
- Diagnosis of sepsis according to criteria defined by The Third International Consensus Definitions for Sepsis and Septic Shock (Sepsis-3) based on:
 - Suspected or confirmed infection
 - SOFA score of 2 or more (excluding renal component)
- Diagnosis of AKI Stage 1 or greater per the following criterion:
 - An absolute increase in serum or plasma creatinine (CR) by ≥ 0.3 mg/dL (≥ 26.5 $\mu\text{mol/L}$) within 48 hours or presumed to have occurred in the previous 48 hours as compared to the reference creatinine baseline as below:

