A total of approximately 20 participants will be randomized for the study. After informed consent is obtained from the participant/legal representative and the participants' eligibility is confirmed, study sites will perform the screening and baseline (Day 1) assessments following the assessment schedule (Table 1-2). Participants will be randomly assigned to receive either TIN816 at 2 mg/kg or placebo using a 3:1 allocation ratio (TIN816:placebo). A single dose of the study treatment will be administered via 2-hour IV at the randomization visit in a participant and investigator-blinded fashion. The study treatment must be administered within 48 hours, after SA-AKI is first diagnosed, but ideally as soon as possible. Two PK samples will be taken at Day 1, one prior to study treatment and one immediately after the completion of IV infusion (within 15 minutes), and additional samples will be taken at Day 2, 3, 5, 8, 14, 30, 60 and 90, optimally always at the same time of the day as when dosing of TIN816 started on Day 1. All participants will be followed-up for a total duration of 90 days.

An interim analysis is planned when approximately 8 participants complete Day 14 visit. The study will continue without modification if a similar PK profile of TIN816 compared to that in the HV is confirmed. Otherwise, an adaptive design would be implemented with options to add up to two additional arms testing a higher dose, multiple bolus doses, extended infusion dosing regimens or combination of bolus dose and extended infusion. The adaptive design will be supported by modeling and simulation with data from the preclinical studies, FIH study and the interim analysis of the current PK/PD study. Patient recruitment will continue during the IA to enroll up to a cap of 12 patients. In the circumstance that the first IA does not provide sufficient PK data to support phase 2b, an additional IA will be added when all 20 patients complete Day 14 visit.

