6.7 Treatment of overdose

Study treatment overdose is the administration of a quantity of the investigational medicinal product which is above the maximum recommended dose according to study protocol.

In the event of an overdose, the treating physician, in collaboration with the investigator should:

- Contact the medical monitor immediately.
- Closely monitor the participant for any AE/SAE and laboratory abnormalities until study drug can no longer be detected systemically (at least 38 days).
- Obtain a plasma sample for PK analysis (within 15 minutes after infusion interruption or infusion end, the latter marking the first PK time point post-dose).
- Document the quantity of the excess dose.

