9.3.1 Definition of primary endpoint(s)

The primary endpoint is all PK related parameters (Table 9-1). The analyses will be performed on PK population set.

TIN816 serum concentration data will be listed by treatment, participant and visit/sampling time point. Descriptive summary statistics of TIN816 serum concentration data will be provided by treatment, and visit/sampling time point, including the frequency of concentrations below the LLOQ and reported as zero.

Summary statistics will include mean (arithmetic and geometric), Standard Deviation (SD), CV (arithmetic and geometric), median, minimum and maximum. An exception to this is T_{max} where median, minimum, and maximum will be presented. PK data will also be represented graphically (including spaghetti plots, boxplots and mean plots with SD) by treatment arm, participant and visit.

Drug concentrations below LLOQ will be treated as missing for the calculation of the geometric means and geometric CV%, and as zero for all other calculations including calculation of PK parameters. Pharmacokinetic parameters will be calculated as described in [Section 8.7](#) and will be listed by treatment and participant and summarized by treatment with descriptive statistics as listed below.

The pharmacokinetic parameters listed in the table below will be determined from the serum concentration time data using the actual recorded sampling times and non-compartmental method(s) with Phoenix WinNonlin (Version 6.4 or higher). Other relevant PK parameters may be added (data permitting).

Table 9-1 Non-compartmental pharmacokinetic parameters

PK parameter	Definition
AUC_{last}	The AUC from time zero to the last measurable concentration sampling time (t_{last}) (mass \times time \times volume $^{-1}$)
AUC_{inf}	The AUC from time zero to infinity (mass \times time \times volume $^{-1}$)
C_{max}	The maximum (peak) observed serum drug concentration after single dose administration (mass \times volume $^{-1}$)

T_{max}	The time to reach maximum (peak) serum drug concentration after single dose administration (time)
$T_{1/2}$	The elimination half-life associated with the terminal slope (λz) of a semi logarithmic concentration-time curve (time). Use qualifier for other half-lives
Cl	The total body clearance of drug from the serum following intravenous administration (volume \times time $^{-1}$)
V_z	The apparent volume of distribution during terminal phase following intravenous administration (associated with λz) (volume)

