9.9.1 Primary endpoint(s)

The proposed sample size of 15 participants in TIN816 study treatment arm is sufficient to achieve a target margin of error not larger than 15% of the geometric mean (half-width of a 2-sided 95% confidence interval for the PK parameters) assuming geometric coefficient of variant (GCV) is 0.25 in AUC_{inf} or C_{max} . It will also be able to exclude a 1.5-fold change in AUC_{inf} or C_{max} assuming GCV increased variability of 0.75.

Different GCV rates and corresponding precision of confidence interval are shown in below table.

Table 9-2 Sensitivity of confidence interval precision to change in assumption for GCV rate

GCV rate *	Width of 95% confidence interval
0.25	[GCV mean/1.15, GCV mean x 1.15]
0.50	[GCV mean/1.31, GCV mean x 1.31]
0.75	[GCV mean/1.47, GCV mean x 1.47]

*GCV mean of AUC_{inf} and C_{max} for 2 mg/kg are 8% and 22%, respectively in FIH study (CTIN816A02101) interim safety reports

10 Supporting documentation and operational considerations

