2.5.1 Primary endpoint(s)/Primary estimand(s)

The primary endpoint is all TIN816 concentrations in serum PK parameters, including C_{max} , T_{max} , $T_{1/2}$, Cl , V_z , AUC_{last} and AUC_{inf} , and other relevant PK parameters (data permitting) (Table 2-1). It will be summarized descriptively for participants with at least one dose of study treatment.

There is no inferential analysis to be performed.

TIN816 serum concentration data will be listed by treatment, participant and visit/sampling time point. Descriptive summary statistics of TIN816 serum concentration data will be provided by treatment, and visit/sampling time point, including the frequency of concentrations below the LLOQ and reported as zero.

Summary statistics will include mean (arithmetic and geometric), standard deviation (SD), CV (arithmetic and geometric), median, minimum and maximum. An exception to this is T_{max} where median, minimum, and maximum will be presented. PK data will also be represented graphically (including spaghetti plots, and mean plots with SD) by treatment arm, participant and visit. Overlaying individual serum concentration-time profiles will be generated by treatment arm participant and visit/sampling time point.

Drug concentrations below LLOQ will be treated as missing for the calculation of the geometric means and geometric CV%, and as zero for all other calculations including calculation of PK parameters. Pharmacokinetic parameters will be calculated as described in CTIN816B12201 Protocol and will be listed by treatment and participant and summarized by treatment with descriptive statistics as listed below.

The pharmacokinetic parameters listed in the table below will be determined from the serum concentration time data using the actual recorded sampling times and non-compartmental method(s) with Phoenix WinNonlin (Version 6.4 or higher). Other relevant PK parameters may be added (data permitting).

Table 2-1 Pharmacokinetic parameters from Non-compartmental analysis

PK parameter	Definition
AUC_{last}	The area under the curve (AUC) from time zero to the last measurable concentration sampling time (T_{last}) (mass \times time \times volume-1)
AUC_{inf}	The AUC from time zero extrapolated to infinity (mass \times time \times volume-1)
AUC_{inf} / D	The AUC from time zero to infinity (mass \times time \times volume-1), normalized by actual dose (mg/kg)
AUC_{0-14d}	The AUC from time zero to 14 days post-dose (mass \times time \times volume-1)

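### The linear trapezoidal rule, applied to sampling gaps of 16 to 30 days after Day 14, overstates AUC and understates CL and Vz by a moderate, avoidable amount

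*Protocol*

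**What the plan says.** Protocol section 8.7 (Pharmacokinetics) fixes the integration method: "The linear trapezoidal rule will be used for AUC calculation, starting with the initiation of IV infusion". It gives no separate rule for the declining part of the curve. SAP section 2.5.1 adopts this by reference: "Pharmacokinetic parameters will be calculated as described in CTIN816B12201 Protocol". SAP section 4, which lists changes to the protocol's analyses, leaves the rule alone.

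Serum is sampled before dosing, at the end of the 2-hour infusion, and "also at Day 2, 3, 5, 8, 14, 30, 60 and 90" (Protocol section 1.1; section 4.1 agrees). Section 8.7 anchors the clock: "Day 2 sample should be taken 24 h after starting TIN816/placebo infusion". Days 14, 30, 60 and 90 are therefore 13, 29, 59 and 89 days after the start of dosing, and the last three gaps are 16, 30 and 30 days.

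AUClast, AUCinf, CL and Vz are among the seven primary PK parameters (Protocol Table 9-1). No sensitivity analysis is planned (Protocol section 9.3.5, SAP section 2.5.5).

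**The concern.** Once the infusion ends, concentration falls along a convex curve. A chord between two points on such a curve lies above it, so the linear rule overestimates every declining interval and the errors add up. The error grows with the gap measured in half-lives, and the gaps after Day 14 are long. AUClast and AUCinf come out too high. CL (dose divided by AUCinf) and Vz (CL divided by the terminal slope) come out too low. Cmax, Tmax and T1/2 do not depend on the rule.

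The primary objective is to describe exposure, summarised by the geometric mean. With no inferential test planned, the exposure values are themselves the primary result and will inform later dosing. A systematic error in them is not reduced by enrolling more participants.

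**Working it through.** **The plan's own yardstick.** Section 9.9.1 sizes the TIN816 arm (n = 15) for a "target margin of error not larger than 15% of the geometric mean" at a geometric CV of 0.25. The confidence factor is exp(t × σ/√n), with σ = √ln(1 + GCV²) and t the 0.975 quantile on n − 1 df. With n = 15, GCVs of 0.25, 0.50 and 0.75 give 1.146, 1.299 and 1.448. The 15% claim holds. The printed 1.15, 1.31 and 1.47 match n = 14 (1.153, 1.314, 1.471), a side point that does not matter here.

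**Inputs.** From the documents: 2-hour infusion, nominal sampling times 0 and 2 h and 1, 2, 4, 7, 13, 29, 59 and 89 days, LLOQ 10 ng/mL, at least three points after Cmax for the terminal slope. Assumed, because the documents do not give them: end-of-infusion peak 20, 40 or 60 µg/mL, and the half-life.

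**Formulae.** With k = ln 2/T1/2, the true area of a declining interval is (C1 − C2)/k and the linear area is (C1 + C2)/2 × Δt. The tail beyond the last quantifiable sample is C_last/k.

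**Worked case: T1/2 = 5 days, peak 40 µg/mL.** Here k = 0.1386 per day and the true AUCinf is 290.2 µg·day/mL.

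| Interval (days) | Linear area | True area | Excess, % of AUCinf |
|---|---|---|---|
| 0 to 7 | 180.9 | 179.6 | 0.4 |
| 7 to 13 | 66.0 | 62.5 | 1.2 |
| 13 to 29 | 59.2 | 42.9 | 5.6 |
| 29 to 59 | 11.1 | 5.2 | 2.0 |

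The sum is +9.3%, of which 7.7 points arise after Day 14. CL and Vz change by 1/1.093 − 1 = −8.5%.

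**One-phase results, peak 40 µg/mL.**

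| T1/2 (days) | Last quantifiable visit | AUCinf bias | Points from gaps after Day 14 | CL and Vz bias |
|---|---|---|---|---|
| 2 | Day 14 | +5.5% | 0 | −5.2% |
| 3 | Day 30 | +8.3% | 4.6 | −7.7% |
| 4 | Day 30 | +8.1% | 5.7 | −7.5% |
| 5 | Day 60 | +9.3% | 7.7 | −8.5% |
| 7.6 | Day 90 | +8.7% | 8.0 | −8.0% |
| 10 | Day 90 | +7.6% | 7.2 | −7.0% |
| 14 | Day 90 | +5.7% | 5.5 | −5.4% |
| 21 | Day 90 | +3.3% | 3.3 | −3.2% |

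At 5 days with a peak of 20 µg/mL, Day 60 falls below the LLOQ and the bias is +7.3%. Over 2 to 21 days and all three peaks, AUCinf bias is +3.3% to +9.3% and AUClast bias +3.5% to +9.3%. Linear-up/log-down gives 0.0%, as it must for an exact exponential.

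**Less favourable shapes for log-down.** Over 660 assumed two-phase curves (terminal T1/2 5 to 10 days, distribution phase 30% to 70% of peak with T1/2 0.25 to 1 day), the linear rule gives +6.7% to +13.0%, with 3.7 to 7.9 points from gaps after Day 14. Log-down gives +0.3% to +2.7%. With 10% to 20% assay noise on one-phase curves (T1/2 3, 5 and 10 days), linear gives +7.1% to +9.0% and log-down −1.0% to −0.2%.

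**Where the half-life might lie.** There are only indirect pointers.
- Protocol section 6.7 asks for monitoring "until study drug can no longer be detected systemically (at least 38 days"). If 38 days is the time to fall from 20–60 µg/mL to 0.01 µg/mL, T1/2 = 38/log2(peak/0.01) = 3.5 to 3.0 days. If it is five half-lives, T1/2 = 7.6 days. Over 3.0 to 7.6 days the bias is +7.0% to +9.3%.
- Protocol section 4.3 mentions about three weeks of effect and ex vivo IC90s of 0.25 and 7.8 µg/mL. With the same peaks, T1/2 = 21/log2(peak/IC90) spans 2.7 to 15.5 days. At 15.5 days the bias is about +5.0%.

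**Against the 15% margin.** On the log scale, the one-phase bias is ln(1.033) to ln(1.093), or 0.033 to 0.089, against ln(1.15) = 0.140: 24% to 64% of the margin. From a noncentral t with 14 df and noncentrality ln(1 + bias) × √15/σ, a nominal 95% interval would cover the true geometric mean 92% to 74% of the time at GCV 0.25, 94% to 90% at 0.50, and 95% to 92% at 0.75.

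**Up to the Day 14 sample.** One-phase AUC is overstated by 5.6% at a half-life of 2 days, 3.9% at 3, 2.7% at 4, and at most 2.0% at 5 days or more. The two-phase range is +1.2% to +7.7%.

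**The case against.** The strongest counter-case is about weight, and several parts of it stand.

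- **No decision depends on it.** The plan reports no confidence interval and tests nothing, so the coverage figures only indicate scale. The 74% needs the largest one-phase bias together with the lowest GCV. The bias is far below the 1.5-fold change that section 9.9.1 aims to exclude.
- **The interim is largely spared.** It uses data to Day 14. SAP Table 2-1 adds an AUC to 14 days that depends little on the later gaps, and the optional population PK model (SAP section 2.5.6) would not use this rule.
- **The size is conditional.** The 38-day pointer may be only a washout convention, and the section 4.3 pointer reaches half-lives with a smaller bias. Among the two-phase shapes +13.0% is extreme: the median is +8.7%, and 11% exceed 10%.
- **The figures describe complete profiles.** The PK set requires survival only past Day 7. In one-phase cases with T1/2 of 3 to 14 days, a profile ending at Day 14 carries an AUCinf bias of only 0.2% to 3.7%. A missing Day 30 sample with later samples present raises it to +20% to +38% at half-lives of 5 to 14 days. The reported mean would mix these.
- **Comparability.** If the first-in-human study used the linear rule with similar sampling, the bias would largely cancel in that comparison, and changing this study alone would create a mismatch. The documents give neither that study's AUC rule nor its sampling times, so this cannot be settled.

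None of these points reverses the direction of the bias or makes the linear rule the better choice for describing exposure in these patients. The comparability risk is real and must be handled in the fix.

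**Conclusion.** The concern holds. On complete profiles the specified rule overstates AUClast and AUCinf and understates CL and Vz. For one-phase decline the AUC bias is about 3% to 9% over half-lives of 2 to 21 days, and about 6% to 9% over 3 to 14 days. It is somewhat larger for some two-phase curves. Gaps after Day 14 cause more than half of the one-phase bias from a half-life of about 3 days; at 2 days all of it comes from earlier gaps.

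The direction follows from convexity. The size rests on assumed half-lives, peaks and curve shapes, and on nominal sampling times. Distortion of the healthy-volunteer comparison is neither shown nor claimed. This is an inexpensive improvement that should be made, not a flaw that undermines the study.

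**What to change.** Replace the sentence in Protocol section 8.7 with: *AUC is computed by the linear-up/log-down trapezoidal method from the start of the infusion.* Record the change in SAP section 4. Compute the first-in-human 2 mg/kg comparator by the same rule. If that study was reported with the linear rule and cannot be rerun, also report this study's linear-rule AUC beside it.

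The cost is one software setting, one sentence and a short rerun on six first-in-human profiles (Protocol section 2.2: six treated participants per cohort). A protocol edit needs a written amendment with the approvals in section 10.1.8.1, so it is best combined with another amendment; SAP section 4 could also carry the change. No new samples or participants are needed. The downside is two AUC versions side by side if the first-in-human data cannot be reanalysed.
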